### 6.3 Oocyte Retrieval

Oocyte retrieval must take place 36h ( $\pm$ 2h) after hCG or GnRH agonist administration. All oocytes from follicles with an estimated diameter  $\geq$ 12 mm should be retrieved. Below are listed the procedures related to the subjects attending the oocyte retrieval visit, while procedures related to the oocytes are described in section 6.4.

The following must take place at the oocyte retrieval visit:

- Blood collection for central laboratory analysis of:
  - endocrine parameter (FSH only)
- Oocyte retrieval
- Dispensing of progesterone for luteal phase support – must be started on the day of oocyte retrieval or the day after and continued at least until clinical pregnancy [*note*: only applicable for subjects who underwent triggering of final follicular maturation with hCG and who had oocytes retrieved]
- Drug accountability of hCG or GnRH agonist, as applicable
- Collection of diary pages
- Recording of use of any concomitant medication
- Recording of adverse events

For subjects with oocytes retrieved following hCG administration, the next visit is the transfer visit 3 days after oocyte retrieval (section 6.5.1).

For subjects with oocytes retrieved following GnRH agonist administration, the oocytes will undergo the procedures described in section 6.4 and embryos will be cryopreserved on day 3, 5 or 6 after oocyte retrieval, according to local practice. The next visit for these subjects is the first post-dosing anti-FSH antibody assessment visit which must be scheduled 5-10 days after the last FE 999049 or GONAL-F dose (section 6.5.2).

For subjects with no oocytes retrieved, the next visit is the first post-dosing anti-FSH antibody assessment visit which must be scheduled 5-10 days after the last FE 999049 or GONAL-F dose (section 6.5.2).

## 6.4 Oocyte / Embryo Evaluation

The laboratory procedures regarding handling and evaluations of oocytes and embryos are described in a trial-specific manual. This section provides an overview of the procedures and assessments to be made from oocyte retrieval till transfer at the embryo stage. The flow of the trial procedures for oocytes is shown in Table 6-3.

**Table 6-3 Trial Flow Chart – Oocyte / Embryo Procedures**

	Day 0 (OR)	Day 1 after OR	Day 3 after OR
Oocyte retrieval (OR)	X		
Assessment of maturity stage (applicable for oocytes undergoing ICSI)	X		
Insemination by IVF or ICSI b	X		
Assessment of oocyte fertilisation		X	
Assessment of embryo quality			X
Transfer of 1 or 2 embryos of the highest quality available: – Subjects <35 years at randomisation: • single embryo transfer if a good-quality embryo is available • double embryo transfer if a good-quality embryo is not available (and if two embryos are available) – Subjects ≥35 years at randomisation: • double embryo transfer (if two embryos are available)			X
Cryopreservation of embryos, as applicable c			X c

Assisted hatching and pre-implantation genetic diagnosis (PGD) / pre-implantation genetic screening (PGS) are prohibited.

### Day 0 (Oocyte Retrieval)

- Assessment of maturity stage (applicable for oocytes undergoing ICSI)
- Insemination at 0h using IVF or ICSI using ejaculated sperm (fresh or frozen) from partner or donor

### Day 1 after Oocyte Retrieval

- Assessment of fertilisation (number of pronuclei)

b Rescue ICSI is not allowed.

c Cryopreservation of surplus embryos can be postponed to day 5 or 6, according to local practice.

### Day 3 after Oocyte Retrieval

- Assessment of embryo quality:
  - Number of cells
  - Compaction status
  - Fragmentation (either 0%, 1-10%, 11-20%, 21-50% or >50% fragmentation, or totally fragmented (no blastomeres recognised))
  - Blastomere uniformity (equally or unequally)
  - Visual signs of multinucleation (yes/no)

Good quality embryo is defined as an embryo with  $\geq 6$  blastomeres and  $\leq 20\%$  fragmentation, without signs of multinucleation

- Transfer of embryo (section 6.5)

Cryopreservation of surplus embryos should be performed on day 3 after oocyte retrieval. Cryopreservation can be postponed to day 5 or day 6 after oocyte retrieval, as applicable and according to local practice.

## 6.5 Transfer

### 6.5.1 Embryo Transfer

Transfer is performed on day 3 (embryo stage) after oocyte retrieval. The subject-related procedures are described below.

- Blood collection for central laboratory analysis of anti-FSH antibodies (first post-dosing assessment)
- Transfer of 1 or 2 embryo(s) of the highest quality available according to this policy:
  - Subjects <35 years at randomisation:
    - single embryo transfer if a good quality embryo is available
    - double embryo transfer if a good-quality embryo is not available (and single transfer if two embryos are not available).
  - Subjects  $\geq 35$  years at randomisation:
    - double embryo transfer (and single transfer if two embryos are not available).

(note: transfer is only applicable for subjects who underwent triggering of final follicular maturation with hCG. Subjects who were administered GnRH agonist will not undergo transfer in the current fresh cycle).

- Dispensing of progesterone for luteal phase support
- Drug accountability of progesterone
- Recording of use of any concomitant medication
- Recording of adverse events

For subjects with embryo transfer, the next visit is the  $\beta$ hCG test visit which must be scheduled 13-15 days after transfer (section 6.6).

### **6.5.2 First Post-dosing Anti-FSH Antibody Assessment (5-10 Days after Last IMP Dose)**

Subjects who have been exposed to FE 999049 or GONAL-F must have the first post-dosing anti-FSH antibody assessment performed 5-10 days after the last FE 999049 or GONAL-F dose. This may coincide with the transfer visit (section 6.5.1).

For subjects who do not attend the transfer visit, a separate visit must be scheduled, at which the following must take place:

- Blood collection for central laboratory analysis of anti-FSH antibodies
- Drug accountability of progesterone
- Recording of use of any concomitant medication
- Recording of adverse events

## **6.6 $\beta$ hCG Test**

### **6.6.1 $\beta$ hCG Test**

Subjects who have undergone transfer must attend a visit 13-15 days after transfer.

The following must take place:

- Blood collection for local laboratory analysis of  $\beta$ hCG
- Blood collection for central laboratory analysis of anti-FSH antibodies (second post-dosing assessment)
- Dispensing of progesterone for luteal phase support, if applicable
- Drug accountability of progesterone
- Recording of use of any concomitant medication
- Recording of adverse events

The blood sample for  $\beta$ hCG will be analysed by the local laboratory and evaluated according to the laboratory's reference ranges. In case of a borderline  $\beta$ hCG result, the test should be repeated.

Subjects with a positive  $\beta$ hCG test must attend a clinical pregnancy visit 5-6 weeks after transfer (section 6.7). Subjects with a negative  $\beta$ hCG test must proceed to the end-of-trial assessments (section 6.9).

### **6.6.2 Second Post-dosing Anti-FSH Antibody Assessment (19-28 Days after Last IMP Dose)**

Subjects who have been exposed to FE 999049 or GONAL-F must have the second post-dosing anti-FSH antibody assessment performed 19-28 days after the last FE 999049 or GONAL-F dose. This may coincide with the  $\beta$ hCG test visit (section 6.6.1).

For subjects who do not attend the  $\beta$ hCG test visit, a separate visit must be scheduled, at which the following must take place:

- Blood collection for central laboratory analysis of anti-FSH antibodies
- Dispensing of progesterone for luteal phase support, if applicable
- Drug accountability of progesterone
- Recording of use of any concomitant medication
- Recording of adverse events

For subjects who do not attend the  $\beta$ hCG test visit, this second post-dosing anti-FSH antibody assessment may be done in connection with the end-of-trial visit (section 6.9).

### **6.7 Clinical Pregnancy**

Subjects with a positive  $\beta$ hCG test must attend a visit 5-6 weeks after transfer.

The following must take place:

- Transvaginal ultrasound of uterus to assess any clinical pregnancy
- Drug accountability of progesterone
- Dispensing of progesterone for luteal phase support, if continued according to local practice
- Recording of use of any concomitant medication
- Recording of adverse events

If at least one gestational sac (either intrauterine or ectopic) is observed, this confirms a clinical pregnancy. If at least one intrauterine gestational sac with fetal heart beat is observed, this confirms a vital pregnancy. For subjects with a vital pregnancy, the next visit is the ongoing pregnancy visit 10-11 weeks after transfer (section 6.8). Subjects with no vital pregnancy must undergo end-of-trial assessments (section 6.9).

### **6.8 Ongoing Pregnancy**

If a vital pregnancy has been documented, the subject must attend a visit 10-11 weeks after transfer.

The following procedures / assessments must take place:

- Ultrasound (transvaginal or abdominal) of uterus to assess any intrauterine viable fetus
- Drug accountability of progesterone, if applicable
- Recording of use of any concomitant medication

- Recording of adverse events

If at least one intrauterine viable fetus is identified, this confirms an ongoing pregnancy.

## 6.9 End-of-trial

If a subject attends the scheduled trial visits, the end-of-trial assessments should take place at the last scheduled trial visit, i.e. for subjects with a confirmed vital pregnancy, the ongoing pregnancy visit would be the last scheduled trial visit and thus the visit where the end-of-trial assessments should be done.

Due to the timing of the mandatory anti-FSH antibody assessments, the end-of-trial assessments can at the earliest be 19-28 days after the last FE 999049 or GONAL-F dose. This may coincide with the  $\beta$ hCG visit for subjects with a negative  $\beta$ hCG test.

The following procedures / assessments must take place at the end-of-trial visit, irrespective of whether the subject discontinues the trial prematurely or completes it:

- Body weight
- Physical examination
- Gynaecological examination
- Vital signs
- Blood collection for central laboratory analysis of
  - clinical chemistry and haematology parameters
  - anti-FSH antibodies (second post-dosing assessment) [*note*: only applicable for subjects who have not already had a blood sample taken for the second post-dosing anti-FSH antibodies assessment as described in sections 6.6.1 and 6.6.2]
- Drug accountability, if applicable
- Recording of use of any concomitant medication
- Recording of adverse events
- Completion of end-of-trial form

These assessments serve to document the subject's physical health at the end of the trial.

## 6.10 Post-trial Activities

### Pregnancy Follow-up

All subjects with an ongoing pregnancy will be followed till delivery to gather information on live birth rate. Furthermore, data will be gathered on neonatal health, including any congenital anomalies, at birth and at 4 weeks after birth as described in section 7.4.1.

## **7 TRIAL ASSESSMENTS**

### **7.1 Assessment Related to Primary Endpoint**

#### **7.1.1 Ongoing Pregnancy**

A transvaginal or abdominal ultrasound of the uterus will be performed 10-11 weeks after transfer. Ongoing pregnancy will be defined as at least one intrauterine viable fetus. For ongoing pregnancies, the number of intrauterine viable fetuses will be recorded.

### **7.2 Assessments Related to Secondary Endpoints**

#### **7.2.1 $\beta$ hCG Test**

A blood  $\beta$ hCG test must be obtained 13-15 days after transfer. If the test is positive according to the local laboratory's reference ranges, this confirms a positive  $\beta$ hCG.

#### **7.2.2 Clinical Pregnancy**

A transvaginal ultrasound of the uterus will be performed 5-6 weeks after transfer. Clinical pregnancy will be defined as at least one gestational sac, either intrauterine or ectopic. The inclusion of ectopic pregnancies and the lack of specification of heart beat in the definition of clinical pregnancy is in line with the current International Committee Monitoring Assisted Reproductive Technologies (ICMART) and World Health Organization (WHO) glossary on ART terminology.d,34 For intrauterine and ectopic pregnancies, the number of gestational sacs with fetal heart beat as well as without fetal heart beat will be recorded.

#### **7.2.3 Vital Pregnancy**

A transvaginal ultrasound of the uterus will be performed 5-6 weeks after transfer. Vital pregnancy will be defined as at least one intrauterine gestational sac with fetal heart beat 5-6 weeks after transfer.

#### **7.2.4 Implantation**

Implantation is determined based on the transvaginal ultrasound performed at the clinical pregnancy visit. Implantation rate will be defined as the number of gestational sacs 5-6 weeks after transfer divided by number of embryos transferred.

#### **7.2.5 Ongoing Implantation**

Ongoing implantation is determined based on the ultrasound performed at the ongoing pregnancy visit. Ongoing implantation rate will be defined as the number of intrauterine viable fetuses

---

d ICMART and WHO glossary on ART terminology: Clinical pregnancy – a pregnancy diagnosed by ultrasonographic visualization of one or more gestational sacs or definitive clinical signs of pregnancy. It includes ectopic pregnancy.

10-11 weeks after transfer divided by number of embryos transferred.

### **7.2.6 Extreme Ovarian Response**

The number of oocytes retrieved will be counted at the oocyte retrieval visit. Extreme ovarian response will be defined as retrieval of  $<4$ ,  $\geq 15$  or  $\geq 20$  oocytes.

### **7.2.7 Early OHSS (including OHSS of Moderate/Severe Grade) and/or Preventive Interventions for Early OHSS**

Early OHSS is defined as OHSS with onset  $\leq 9$  days after triggering of final follicular maturation. Classification of grade is according to Golan's classification system (see section 8.3 for details) and all OHSS cases will be graded as mild, moderate or severe. Preventive interventions for early OHSS cover cycle cancellation due to excessive ovarian response or triggering of final follicular maturation with GnRH agonist.

### **7.2.8 Cycle Cancellation due to Poor or Excessive Ovarian Response or Embryo Transfer Cancellation due to Excessive Ovarian Response / OHSS Risk**

The reason for each cycle cancellation will be recorded. Cycle cancellations related to inappropriate ovarian response will include poor and excessive follicular development. Cycle cancellation due to poor follicular development is implemented when the investigator judges that  $\geq 3$  follicles with a diameter  $\geq 17$  mm cannot be reached by stimulation day 20. Cycle cancellation due to excessive follicular development is implemented when  $>35$  follicles with a diameter  $\geq 12$  mm are observed (can also be implemented if there are 25-35 follicles with a diameter  $\geq 12$  mm). The reason for each embryo transfer cancellation will be recorded. Transfer cancellation due to adverse events such as the Medical Dictionary for Regulatory Activities preferred terms (MedDRA PTs) "ovarian hyperfunction" and "ovarian hyperstimulation syndrome" and "high progesterone" in subjects with embryos available for transfer will be considered as transfer cancellations due to excessive response / OHSS risk.

### **7.2.9 Number and Size of Follicles during Stimulation**

Transvaginal ultrasound will be performed at all visits during the stimulation period to count the number of follicles and measure the size of the follicles. Data will be recorded separately for the right and left ovary.

### **7.2.10 Number and Distribution of Oocytes Retrieved**

The number of oocytes retrieved will be recorded at the oocyte retrieval visit. The proportion of subjects with  $<4$  oocytes (low response), 4-7 oocytes (moderate response), 8-14 oocytes (targeted response), 15-19 oocytes (hyperresponse) and  $\geq 20$  oocytes (severe hyperresponse) will be calculated.

### **7.2.11 Metaphase II Oocytes**

Maturity stage will be assessed prior to insemination for oocytes that will undergo ICSI. Maturity

stage will be categorised as germinal vesicle, metaphase I, metaphase II, degenerated or other.

### **7.2.12 Fertilisation Rate**

The number of pronuclei will be counted on day 1 after oocyte retrieval and recorded as 0, 1, 2 or >2. Fertilised oocytes with 2 pronuclei will be regarded as correctly fertilised.

### **7.2.13 Number and Quality of Embryos on Day 3**

Each embryo will be followed closely and formally evaluated on day 3 after oocyte retrieval. The quality evaluation will consist of assessment of cleavage stage and embryo morphology parameters (number of cells, degree of fragmentation, blastomere uniformity and visual signs of multinucleation).

Cleavage stage will be defined by the number of blastomeres: 1, 2, 3, 4, 5, 6, 7, 8, .... On day 3, it will also be possible to indicate the compaction status instead of number of blastomeres.

Degree of fragmentation will be classified as one of the following: 0%, 1-10%, 11-20%, 21-50%, or >50% fragmentation, or totally fragmented (no blastomeres recognised).

Blastomere uniformity will be classified as equally sized blastomeres or unequally sized blastomeres (largest blastomere >25% larger in average diameter compared to the smallest blastomere).

Visual sign of multinucleation will be evaluated as yes or no.

A good quality embryo is defined as an embryo with  $\geq 6$  blastomeres and  $\leq 20\%$  fragmentation, without signs of multinucleation.

### **7.2.14 Circulating Levels of Endocrine Parameters**

During treatment, the following panel of endocrine parameters will be evaluated (treatment panel): FSH, LH, estradiol, progesterone, inhibin A and inhibin B.

Blood samples will be drawn at stimulation day 1e, stimulation day 6 and the end-of-stimulation visit. The sample on stimulation day 1 (baseline) will be collected prior to the first dose of FE 999049 or GONAL-F, and samples drawn at stimulation day 6 and the end-of-stimulation visit will be collected at least 8 hours after the previous FE 999049, GONAL-F or GnRH antagonist administration. The samples will be analysed at a central laboratory. The investigator will review and evaluate the laboratory results. The Laboratory Report will be signed and dated by the investigator.

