## 6.2 Stimulation

### 6.2.1 Stimulation Day 1

Subjects will attend the stimulation day 1 visit on day 2-3 of the menstrual cycle.

The following must take place prior to randomisation:

- Ensure that the subject is still eligible for participation in the trial
- Check those inclusion and exclusion criteria that were not possible during screening
- Body weight [*note*: this body weight result is used for dose calculation in the FE 999049 group and should be measured on a trial specific calibrated scale]
- Pregnancy test – must be negative
- Transvaginal ultrasound of uterus and ovaries (endometrial thickness, ovarian volume, number and size of follicles). If a cyst  $\geq 10$  mm is observed (functional or not), it should be punctured before treatment is initiateda. If the cyst was present at the screening visit, it should have been recorded on the medical history form. If the cyst presented between screening and stimulation day 1, it should be recorded on the adverse event form.

If the subject fulfils all inclusion and exclusion criteria, she will proceed to randomisation:

- Randomisation, i.e. assignment to the lowest available subject number and thereby allocation to either FE 999049 or GONAL-F

The following must take place after randomisation but before administration of the first dose of IMP (FE 999049 or GONAL-F):

- Vital signs (systolic blood pressure, diastolic blood pressure, pulse)
- Blood collection for central laboratory analysis of:
  - Clinical chemistry and haematology parameters
  - Endocrine parameters (AMH and treatment panel: FSH, LH, estradiol, progesterone, inhibin A and inhibin B)
  - Anti-FSH antibodies

Once the above has been completed, the following must be performed by the trial medication delegate. Care must be taken to ensure blinding of the investigator and other assessors.

- Dispense IMP according to randomisation and instruct the subject on how to administer the IMP
- Administer the 1st dose of IMP according to randomisation [administration of IMP takes place at the clinic and can be done by either the trial medication delegate or the subject under supervision by the trial medication delegate]:

---

a Treatment can be initiated the same day. If puncture is not possible, randomisation may be postponed to the next menstrual cycles, assuming that the cyst will disappear and that the subject fulfils the inclusion criteria.

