### **7.2.15 FSH Population Pharmacokinetics**

In addition to the sampling time points mentioned in section 7.2.14, blood samples will also be drawn at the oocyte retrieval visit for analysis of FSH.

Based on the serum FSH samples obtained during the trial, a population pharmacokinetic model will be developed to assess the pharmacokinetics of FE 999049 and confirm predictors for FSH

---

e AMH will also be included in the stimulation day 1 analyses.

concentration levels, such as body weight.

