### **7.3.10 Endocrine Parameters at Screening**

At screening, the following panel of endocrine parameters will be evaluated (screening panel): AMH, TSH and prolactin. The sample will be analysed at a central laboratory.

The results of the screening panel must be available prior to randomisation. The investigator will review and evaluate the laboratory results (with the exception of AMH, which will not be made available to the investigator). The Laboratory Report will be signed and dated by the investigator.

The AMH samples collected at screening may be used for correlation analysis of Elecsys® AMH immunoassay results determined at provincial local laboratories versus the central laboratory.

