#### **Trial-specific Source Data Requirements - Ferring**

Source documents need to be preserved for the maximum period of time permitted by local requirements. For each subject enrolled, the investigator will indicate in the source documents that the subject participates in this trial, and will record at least the following information, if applicable:

- Existence of subject (initials, date of birth)
- Confirmation of participation in trial (trial ID, subject ID)
- Informed consent(s) (date and time of oral information, date and time of handing out Informed Consent Documents, date and time of obtaining written informed consent(s))
- Eligibility for participation in the trial (documenting all inclusion / exclusion criteria)
- Relevant medical history, infertility history, menstrual history and reproductive history
- Body weight measurements
- Visit dates
- Any assessment performed, i.e. vital signs, physical examination, TVU, etc.
- Dates of administration of IMP
- Dates and daily doses of NIMP
- Dates and daily doses of concomitant medication
- Date of oocyte retrieval and number of oocytes retrieved
- Date of transfer and number and quality of embryos transferred
- Results of  $\beta$ hCG test and ultrasound at clinical and ongoing pregnancy visits

- Pregnancy outcome, i.e. live birth or pregnancy loss, and neonatal health at birth and 4 weeks after birth
- Local tolerability reactions after IMP administration – diary
- Adverse events (description as well as start/stop date and time)
- OHSS symptoms, preventive interventions, investigations and treatments
- Reason for discontinuation
- Event of unblinding, including the reason for unblinding

No specific protocol data can be recorded directly in the e-CRF without prior written or electronic record.

If the trial sites use electronic subject record systems, the sponsor will decide if the electronic subject records qualify for the trial and document the decision. If the electronic subject records system does not qualify for the trial, it may be considered to utilise certified printouts of the data in the electronic subject records system for source data as an exception.

The source data for the endocrine parameters, clinical chemistry and haematology parameters will be available at the central laboratory. Laboratory reports will be available at the sites.

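### AMH is withheld from the investigator only at screening: day 1 AMH and on-treatment FSH go to the investigator for review without exception

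*Protocol*

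**What the plan says.** **Screening.** Protocol section 7.3.10 has the investigator review the screening panel (AMH, TSH, prolactin) "with the exception of AMH, which will not be made available to the investigator".

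**Stimulation day 1.** Section 6.2.1 lists an endocrine sample of AMH plus the treatment panel, which includes FSH, under the instruction "The following must take place after randomisation but before administration of the first dose of IMP". Footnote e to section 7.2.14 confirms it: "AMH will also be included in the stimulation day 1 analyses".

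**Day 1, day 6 and end-of-stimulation.** Section 7.2.14 covers all three time points and says "The investigator will review and evaluate the laboratory results", then "The Laboratory Report will be signed and dated by the investigator". No analyte is excepted. Section 7.2.15 adds an FSH sample at oocyte retrieval and does not say who sees the result.

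**Where reports are held.** Section 10.1 says of endocrine and safety laboratory data: "Laboratory reports will be available at the sites".

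**Blinding provisions.** Sections 3.5.3 and 5.6.1 restrict the allocation modules of the e-CRF, the accountability forms, the randomisation list and what subjects may tell the investigator. Beyond that they ask for precaution in general terms. Neither section, nor the definition of assessor-blind in SAP section 1.1.1, mentions laboratory results.

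**The concern.** The plan shields the investigator from AMH at one time point and hands over the same analyte at the next, together with on-treatment FSH. AMH and body weight determine the FE 999049 dose through Table 5-1, while every GONAL-F subject receives 150 IU on days 1 to 5. A reader who has AMH, weight and a day 6 FSH value therefore has some information about which arm produced that value.

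The assessor-blind is the only blind in this trial, since subjects, monitors and the trial medication delegate know the allocation. Investigators keep real discretion: dose-adjustment requests, cancelling or triggering when only 1 or 2 follicles reach 17 mm, and the choice at 25 to 35 follicles. They also grade OHSS and judge adverse event causality. Assessor unblinding heads the list of major deviations (protocol section 9.3, SAP section 5) that remove a subject from the PP set, and non-inferiority must hold in PP as well as in FAS.

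**Working it through.** The plan states no figure on this point, so there is none to reproduce. The check has three steps: does any passage close the gap, how far apart are the doses, and when do the results arise.

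**1. The text.** The exception in 7.3.10 is attached to the screening panel. The review-and-sign sentences in 7.2.14 repeat those of 7.3.10 without it. No passage in the blinding, laboratory or source-data sections restores it.

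**2. The dose contrast on days 1 to 5.**

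Inputs: the GONAL-F pen holds 900 IU = 66 µg (Table 5-4), and the starting dose is 150 IU (Table 5-2). FE 999049 doses, with limits of 6 and 12 µg, come from Table 5-1. Pen rounding is to the nearest 0.33 µg (section 5.1.1).

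GONAL-F by mass: 150 × 66 / 900 = 11.0 µg per day, for every subject.

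FE 999049 at 60 kg is the µg/kg dose × 60, rounded to the pen scale:

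| AMH (pmol/L) | Calculation | Dose (µg) | Ratio to 11 µg |
|---|---|---|---|
| <15 | fixed | 12 | 1.09 |
| 15-16 | 0.19 × 60 = 11.4 | 11.33 | 1.03 |
| 17 | 0.18 × 60 = 10.8 | 10.67 | 0.97 |
| 18 | 0.17 × 60 = 10.2 | 10.33 | 0.94 |
| 28-32 | 0.12 × 60 = 7.2 | 7.33 | 0.67 |
| ≥40 | 0.10 × 60 = 6.0 | 6.0 | 0.55 |

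The arms are within about 10% by mass up to AMH 18 and diverge above that.

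**3. What one FSH value could tell.** The documents give no FSH concentrations, so this is an illustration under assumptions and not an estimate for the trial. Assume that exposure is proportional to mass in both products, that FSH is lognormal with a between-subject CV of 20% to 40%, and that the reader knows the level expected in each arm. With 1:1 allocation and dose ratio r, the chance of a correct guess is Φ(|ln r| / 2σ), where σ = √ln(1 + CV²). Chance alone gives 50%.

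- r = 0.55: 94% (CV 20%) to 78% (CV 40%)
- r = 0.67: 85% to 70%
- r = 1.09: 59% to 54%

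**4. Timing.** Day 6 blood is drawn at the same visit as the first possible dose-change request and goes to a central laboratory. End-of-stimulation blood is drawn at the visit where the trigger or cancellation criterion is met, and retrieval blood after triggering. Unless results return the same day, only the day 6 FSH value can reach the investigator before the trigger decision, and only if it is reported before stimulation ends. Later FSH values could bear only on later judgements such as OHSS grading or causality. No turnaround time is given.

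**The case against.** The strongest reply is that the gap has little practical consequence. Much of that stands:

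- Day 1 AMH is drawn before the first dose and is a baseline value in both arms. It cannot disclose allocation by itself. Being drawn after randomisation, it cannot affect eligibility or selection either.
- Dose requests are to rest on follicular development (section 5.6.1), and triggering and cancellation on follicle criteria (Table 6-2).
- Mass is a weak proxy for serum FSH. The protocol itself describes differences in glycosylation and sialylation between the products. Subjects may enter with early-follicular FSH of 1 to 15 IU/L, and body weight is expected to predict FSH levels.
- The primary endpoint is an ultrasound finding at 10 to 11 weeks, so any bias would act indirectly, through cycle management.
- A laboratory manual may already mask these results, although neither document says so.

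A reader might go further and infer that the day 1 result unblinds the investigator, or that disclosure lets the investigator tailor only the comparator. The documents support neither. The first needs on-treatment FSH and an unknown exposure relationship. The second describes the declared regimen: requests are implemented only for GONAL-F even under perfect blinding. Better tailoring of the comparator would also tend to work against a non-inferiority claim. Nor does the protocol say why screening AMH is withheld, so its purpose as a safeguard against unblinding is an inference.

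The inconsistency survives all of this. As written, the plan gives the investigator a result that it deliberately withholds at screening, together with the on-treatment FSH values that could make it informative.

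**Conclusion.** The point holds as a gap in the assessor-blind. Allocation has not been shown to be revealed. The possible hint is confined to higher-AMH subjects: at 60 kg the FE 999049 dose is 55% of the comparator mass at AMH 40 or more and 67% at AMH 30, but 94% to 109% at AMH 18 or below. How many subjects fall in the range where it matters is unknown, because no AMH distribution is given. The degree of unblinding cannot be quantified without FSH concentrations, between-subject variability and the relative exposure of the two products. An effect on stimulation, triggering or cycle cancellation also needs the day 6 result to be reported in time. The gap is worth closing because it is cheap to close, and it does not by itself call the primary comparison into question.

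**What to change.** Carry the 7.3.10 exception into sections 7.2.14 and 7.2.15. State that day 1 AMH and all post-dose FSH results (day 6, end-of-stimulation and oocyte retrieval) are not released to the investigator or other blinded assessors until database lock. All other endocrine results and all safety laboratory results are released as now. The statement on site-held reports in section 10.1 should refer to the same restriction.

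The cost is a central laboratory reporting setting and a sentence or two of protocol text. Investigators would review and sign those two analytes later. No decision described in the plan depends on them: dose requests, triggering and cancellation use follicle findings, the OHSS work-up in section 8.3.1 uses progesterone and estradiol, and the endocrine alert criteria in SAP Appendix 1 cover only LH and progesterone. Sample size, dosing and the primary analysis are unchanged.
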